9.3 Subject Identification and Privacy

A unique subject number will be assigned to each subject at inclusion, immediately after informed consent has been obtained. This number will serve as the subject's identifier in the trial as well as in the clinical trial database. All subject data collected in the trial will be stored under this number. Only the Investigator will be able to link the subject's trial data to an individual subject via an identification list kept at the site. For each subject, original medical data will be accessible for the purposes of source data verification by the Monitor, audits and Health Authority inspections, but patient confidentiality will be strictly maintained.

Data protection and privacy regulations will be observed in capturing, forwarding, processing, and storing subject data. Subjects will be informed accordingly, and will be requested to give their consent on data handling procedures in accordance with national regulations.

CCI

9.4 Emergency Medical Support and Subject Card

Subjects will be provided with Emergency Medical Support cards supplied by the trial site for use during trial participation in order to provide clinical trial subjects with a way of identifying themselves as participating in a clinical trial and to give health care providers access to any information about this participation that may be needed to determine the course of medical treatment for the subject. The information provided on the Emergency Medical Support card may include the process for emergency unblinding (if applicable).

The first point of contact for all emergencies will be the clinical trial Investigator caring for the affected subject. The Investigator agrees to provide his or her emergency contact information on the card for this purpose. If the Investigator is available when an event occurs, they will answer any questions. Any subsequent action (for example, unblinding) will follow the standard process established for Investigators.

In cases where the Investigator is not available, the Phase I facility will provide the appropriate means to contact a physician. This includes the provision of a 24-hour contact number at the facility, whereby the health care providers will be given access to an appropriate physician to assist with the medical emergency and to provide support for the potential unblinding of the subject concerned.

9.5 Clinical Trial Insurance and Compensation to Subjects

Insurance coverage will be provided for each country participating to the trial. Insurance conditions shall meet good local standards, as applicable.

9.6 Independent Ethics Committee (Human Research Ethics Committee)

Prior to commencement of the trial at a given site, this clinical trial protocol will be submitted together with its associated documents (eg, the PICF) to the responsible HREC for its favorable opinion or approval, which will be filed in the Investigator Site File. A copy will be filed in the Sponsor Trial Master File at the CRO.

The HREC will provide an approval letter that will clearly identify the trial number and list all documents and their version numbers that were reviewed and approved by the committee (eg, the clinical trial protocol and PICF).

Amendments to this clinical trial protocol will also be submitted to the concerned HREC, before implementation of substantial changes (see Section 10.5). Relevant safety information will be

submitted to the HREC during the course of the trial in accordance with national regulations and requirements.

9.7 Health Authorities

The clinical trial protocol and any applicable documentation (for example, IMP Dossier and PICF) will be submitted or notified to the Health Authorities in accordance with all local and national regulations for the trial site.

For Australia: the IB, PICF, clinical trial protocol, and Expert toxicology report will be submitted to HREC for approval and after approval, notified to the Health Authorities, using the CTN scheme, in accordance with all local and national regulations for the trial site.

10 Trial Management

10.1 Case Report Form Handling

Refer to the Manual of Operations for eCRF Completion Guidelines.

The main purpose of the eCRF is to obtain data required by the clinical trial protocol in a complete, accurate, legible and timely. The data in the eCRF should be consistent with the relevant source documents.

The Investigator or designee is responsible for ensuring that the data collected in the course of this trial is accurate and documented appropriately on all applicable forms. They will then be processed, evaluated, and stored in anonymous form in accordance with applicable data protection regulations. The Investigator must ensure that the eCRFs and any other associated documents forwarded to Sponsor or its designated organization contain no mention of any subject names.

The data will be entered into a validated database. The Sponsor or its designee will be responsible for data processing, in accordance with the Sponsor's data management procedures. Database lock will occur once quality control and quality assurance procedures have been completed. PDF files of the eCRFs will be provided to the Investigators at the completion of the trial.

10.2 Source Data and Subject Files

The Investigator must keep a file (medical file, original medical records) on paper or electronically for every subject in the trial. It must be possible to identify each subject by using this subject file. This file will contain the demographic and medical information for the subject listed below and should be as complete as possible.

- Subject's full name, date of birth, sex, height, weight, and skin type
- Medical history and concomitant diseases
- Prior and concomitant therapies (including changes during the trial)
- Trial identification, that is, the Sponsor trial number for this clinical trial, and subject number

- Dates for entry into the trial (informed consent) and visits to the site
- Any medical examinations and clinical findings predefined in this clinical trial protocol
- All AEs observed in the subject, including severity, relationship and outcome of AEs
- Date that the subject left the trial including any reason for early withdrawal from the trial or IMP (if applicable).

All documents containing source data must be filed, including, but not limited to the original printouts of the data recorded or generated by automated instruments, photographic negatives, ECG recordings, and laboratory results. Such documents must bear the subject number and the date of the procedure. If possible, this information should be printed by the instrument used to perform the assessment or measurement. Information that cannot be printed by an automated instrument will be entered manually. As necessary, medical evaluation of such records should be performed; all evaluations should be documented, signed, and dated by the Investigator.

Electronic subject files will be printed whenever the Monitor performs source data verification. Printouts must be signed and dated by the Investigator, countersigned by the Monitor and kept in a safe place at the site.

10.3 Investigator Site File and Archiving

Upon initiation of the trial, the Investigator will be provided with an Investigator Site File containing all necessary trial documents, which will be completed throughout the trial and updated as necessary. The file must be available for review by the Monitor, during Sponsor audits and for inspection by Health Authorities during and after the trial, and must be safely archived for at least 15 years (or longer, per local requirements or as otherwise notified by the Sponsor) after the end of the trial. The documents to be archived include the Subject Identification List and the signed subject PICFs. If archiving of the Investigator Site File is no longer possible at the site, the Investigator must notify the Sponsors/designees.

All original subject files (medical records) must be stored at the site (hospital, research institute, or practice) for the longest possible time permitted by the applicable regulations, and/or as per ICH GCP guidelines, whichever is longer. In any case, the Investigator should ensure that no destruction of medical records is performed without the written approval of the Sponsor.

10.4 Monitoring, Quality Assurance and Inspection by Health Authorities

This trial will be monitored in accordance with the ICH GCP and any other applicable regulations. The site Monitor will perform visits to the trial site at regular intervals.

The clinical trial protocol, each step of the data capture procedure, and the handling of the data, including the final clinical trial report, will be subject to independent Quality Assurance activities. Audits may be conducted at any time during or after the trial to ensure the validity and integrity of the trial data. Representatives of the Quality Assurance unit from the Sponsor or a designated organization, as well as Health Authorities, must be permitted to access all trial documents and

other materials at the site, including the Investigator Site File, the completed eCRFs, all IMP and IMP accountability records, and the original medical records or files for each subject.

10.5 Changes to the Clinical Trial Protocol

Changes to the clinical trial protocol will be documented in written clinical trial protocol amendments. Major (substantial, significant) amendments will usually require submission to the relevant HREC for approval. In such cases, the amendment will be implemented only after approval or favorable opinion has been obtained.

Minor (nonsubstantial) protocol amendments, including administrative changes, will be filed by the trial site. They will be submitted to the relevant HREC or to Health Authorities only where requested by pertinent regulations. Any amendment that could affect the subject's agreement to participate in the trial requires additional informed consent prior to implementation following the process as described in Section 9.2.

10.6 Clinical Trial Report and Publication Policy

10.6.1 Clinical Trial Report

After completion of the trial, a clinical trial report will be written by the Sponsors/designees in consultation with the PI following the guidance in ICH Topic E3.

CCI

| ALT                         | Alanine aminotransferase  |
| AST                         | Aspartate aminotransferase  |
| AUC                         | Area under the curve  |
| AUC 0-24h        | AUC from time zero (= dosing time) to 24 hours postdose   |
| AUC 0-24h /Dose  | Dose-normalized AUC 0-24h  |
| AUC 0-144h       | AUC from time zero (= dosing time) to 144 hours postdose  |
| AUC 0-144h /Dose | Dose-normalized AUC 0-144h   |
| AUC 0-t          | AUC from time zero (= dosing time) to the last sampling time (t last ) at which the concentration is at or above the lower limit of quantification |
| AUC 0-t /Dose    | Dose-normalized AUC 0-t  |
| AUC 0-∞          | The AUC from time zero (dosing time) extrapolated to infinity   |
| AUC 0-∞ /Dose    | Dose-normalized AUC 0-∞  |
| AUC extra %      | The AUC from time $t_{last}$ extrapolated to infinity given as percentage of $AUC_{0-\infty}$   |
| BMI                         | Body mass index   |
| CCI                         |   |
| BP                          | Blood pressure  |
| CI                          | Confidence interval   |
| CL/f                        | Apparent total body clearance of drug following extravascular administration, taking into account the fraction of dose absorbed                               |
| C max            | Maximum observed concentration  |
| C max /Dose      | Dose-normalized C max  |
| CRF                         | Case report form  |
| CSR                         | Clinical Study Report   |
| CV%                         | Coefficient of variation  |
| DBS                         | Dried blood spot  |

| DIPLD            | Drug-induced phospholipidosis                    |
|------------------|--|
| EC50             | Half maximal effective concentration             |
| EC 90 | 90% of maximal effective concentration           |
| ECD              | Early Clinical Development                       |
| CCI              |  |
| GCP              | Good Clinical Practice                           |
| GeoCV%           | Geometric coefficient of variation               |
| GeoMean          | Geometric mean                                   |
| IAP              | Integrated Analysis Plan                         |
| CCI              |  |
| CCI              |  |
| ICH              | International Council for Harmonisation          |
| IMP              | Investigational medicinal product                |
| IV               | Intravenous                                      |
| $\lambda_z$      | Terminal first order (elimination) rate constant |
| LLOQ             | Lower limit of quantification                    |
| LOQ              | Limit of quantification                          |
| MAD              | Multiple ascending dose(s)                       |
| Max              | Maximum  |
| Mean             | Arithmetic mean                                  |
| MedDRA           | Medical Dictionary for Regulatory Activities     |
| CCI              |  |
| Min              | Minimum  |
| MPC              | Minimal parasiticidal concentration              |
| mRNA             | Messenger ribonucleic acid                       |
| N                | Number of non-missing observation                |
| ND               | Nondetectable/not detected                       |
| NR               | No result  |
| PCR              | Polymerase chain reaction                        |
| CCI              |  |
| CCI              |  |

7/31

| CCI               |  |
|-------------------|--|
| PK                | Pharmacokinetic(s)   |
| PLD               | Phospholipidosis   |
| CCI               | Theophenpraeon   |
| PT                | Preferred Term   |
| Q1                | 25th percentile  |
| Q3                | 75th percentile  |
| qPCR              | Quantitative PCR   |
| QTc               | QT interval corrected for heart rate   |
| QTcB              | QT interval corrected for heart rate according to Bazett's formula                                 |
| QTcF              | QT interval corrected for heart rate according to Fridericia's formula                             |
|                   |  |
| Rsq               | Goodness of fit statistic for calculation of λ z  |
| SAD               | Single ascending dose(s)   |
| SAE(s)            | Serious adverse event(s)   |
| SAF               | Safety Analysis Set  |
| SAS               | Statistical Analysis System  |
| SD                | Standard deviation   |
| SDTM              | Study Data Tabulation Model  |
| SE                | Standard error   |
| SI                | Système International  |
| SMC               | Safety Monitoring Committee  |
| SOC               | System Organ Class   |
| t>10 ng/mL        | Time above or equal to the predicted M5717 mouse MPC of 10 ng/mL                                   |
| t>3 ng/mL         | Time above or equal to the predicted M5717 mouse MIC of 3 ng/mL                                    |
| t½                | Apparent terminal half-life  |
| TEAE(s)           | Treatment-emergent adverse event(s)  |
| t last | The last sampling time at which the concentration is at or above the lower limit of quantification |
| t max  | Time to reach the maximum observed concentration   |
| ULOQ              | Upper limit of quantification  |
| Vz/f              | Apparent volume of distribution during the terminal phase following extravascular administration   |

# M5717 FIH Trial of SAD, MAD and Malaria Challenge Model in Healthy Subjects MS201618-0013 Version 2.0

| WHO DDE | The Enhanced World Health Organization Drug dictionary |
|---------|--|

#### 3 Modification History

| Unique
Identifier for
Version | Date of
IAP Version | Author                   | Changes from the Previous Version   |
|-------------------------------------|------------------------|--------------------------|---|
| 1.0                                 | 16AUG2018              | PPD
PPD
PPD
PPD | Original document   |
| 2.0                                 | 13MAY2019              | PPD
PPD
PPD        | Update based on the latest Protocol Version 5.0 including Amendment 4  Urine and feces pharmacokinetic analysis (Section 16.1.2.2) to be performed and reported separately  Pharmacodynamic parameter analysis (Section 16.2.1) to be performed and reported separately |

#### 4 Purpose of the Integrated Analysis Plan

The purpose of this Integrated Analysis Plan (IAP) is to document technical and detailed specifications for the final analysis of data collected for Clinical Study Protocol MS201618-0013. Results of the analyses described in this IAP will be included in the Clinical Study Report (CSR). Additionally, the planned analyses identified in this IAP will be included in regulatory submissions or future manuscripts. Any post-hoc, or unplanned analyses performed to provide results for inclusion in the CSR but not identified in this prospective IAP will be clearly identified in the CSR.

The IAP is based upon the Clinical Study Protocol Version 5.0 including Amendment 4 and is prepared in compliance with International Council for Harmonisation (ICH) E9. It focuses on the detailed description of the statistical analyses for safety, pharmacokinetics (PK), pharmacodynamics (PD), and other variables. Part B of the study (multiple ascending doses [MAD]) is designated as optional in the protocol and will not be conducted, so the analysis is not currently defined in this IAP.

#### Objectives and Endpoints 5

The objectives and endpoints below pertain to Part A and Part C only.

|                         | Objective  | Endpoint  | IAP
Section |
|-------------------------|--|---|----------------|
| PART A                  |  |   |                |
| Primary
Objective    | To investigate the safety and tolerability of single ascending oral doses of M5717 | Primary Endpoints  Nature, incidence, and severity of AEs/SAEs, including relationship to study treatment, AEs/SAEs leading to dose modification or discontinuation of study treatment  Incidence of clinically significant changes and abnormalities in safety laboratory parameters (hematology, coagulation, biochemistry [specifically ALT and AST], and urinalysis)  Incidence of clinically significant changes and abnormalities in vital signs (body temperature, BP, heart rate, and respiratory rate) and 12-lead ECG | 15             |
| Secondary
Objectives | To investigate the PK of single ascending oral doses of M5717                      | Secondary Endpoints  • PK parameters for M5717: C max , t max , λ z , t ½ , AUC (AUC D-m , AUC 0-t , and AUC 0-144h ), AUC extra , CL f , V zf , and dose-normalized AUC 0-m , AUC 0-144h , AUC 0-t , and C max , as well as t >10 ng/mL and t >3 ng/mL   | 16.1.2         |

|                         | Objective   | Endpoint  | IAP
Section  |
|-------------------------|---|---|-----------------|
| PART C                  |   |   |                 |
| Primary
Objective    | To characterize the PK/PD relationship between M5717 PK and parasite clearance in healthy subjects following infection with P. falciparum blood stage parasites during the IBSM challenge by assessment of the PK-to-PRR relationship   | Primary Endpoints PRR as observed through qPCR analysis All M5717 PK parameters as defined in Part A or Part B (depending on dosing regimen in Part C)  | 16.2,
16.1.2 |
| Secondary
Objectives | To characterize the PK/PD relationship between M5717 PK and parasite clearance in healthy subjects following infection with P. falciparum blood stage parasites during the IBSM challenge by assessment of the relationship of PK with the PD parameters: PCT, MIC, PCt 1/2 , MPC, lag time, and frequency of recrudescence  To characterize the parasiticidal activity of M5717 on P. falciparum asexual blood stage parasites in the blood of healthy subjects in the IBSM challenge | PCT, MIC, PCt 1/2 , MPC, lag phase     Number and percentage of subjects with recrudescence  | 16.2            |
|                         | To evaluate the safety and tolerability of M5717 in healthy volunteers following infection with P. falciparum blood stage parasites during the IBSM challenge   | Malaria Clinical Score     Nature, incidence, and severity of AEs/SAEs, including relationship to study treatment, AEs/SAEs leading to dose modification or discontinuation of study treatment     Incidence of clinically significant changes and abnormalities in safety laboratory parameters (hematology, coagulation, biochemistry [specifically ALT and AST], and urinalysis)     Incidence of clinically significant changes and abnormalities in vital signs (body temperature, BP, heart rate, and respiratory rate) and 12-lead ECG | 15              |

The analyses of the endpoints will be described in the respective sections for efficacy, safety, PK, PD, or other endpoints, regardless of whether the endpoint is a primary endpoint or not.

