5.3.2 Exclusion Criteria

5.3.2.1 Part A, Part B, and Part C

1. History or presence of clinically relevant respiratory, gastrointestinal, renal, hepatic, hematological, lymphatic, neurological, cardiovascular, psychiatric, musculoskeletal, genitourinary, immunological, dermatological, connective tissue diseases or disorders.
2. History of any malignancy except surgically cured skin cancers.
3. History of relevant drug hypersensitivity, ascertained or presumptive allergy/hypersensitivity to the active drug substance and/or formulation ingredients; history of serious allergic reactions leading to hospitalization or any other allergic reaction in general, which the Investigator considers may affect the safety of the subject and/or outcome of the trial.
4. History of alcoholism or drug abuse.
5. Liver functions tests:
 - a. above the laboratory reference range the day before IMP administration (Day -1) for Part A and Part B
 - b. $\geq 3 \times$ ULN for Inoculum Day 8 in Part C.
6. Creatinine clearance < 90 mL/min as estimated using the Cockcroft and Gault equation at Screening.
7. Semi-supine BP $> 140/90$ mmHg at Day -1 (this may be repeated once).
8. Electrocardiogram shows a QT interval corrected for heart rate according to Fridericia's formula (QTcF) > 450 ms, PR > 210 ms, QRSD > 120 ms at Screening and predose.
9. Consumption of an average weekly intake of > 14 drinks/week for men or > 7 drinks/week for women. One drink is equivalent to 12 g alcohol = 5 ounces (150 mL) of wine or 12 ounces (360 mL) of beer or 1.5 ounces (45 mL) or 80-proof distilled spirits.
10. Positive for hepatitis B surface antigen, hepatitis B core antibody, hepatitis C antibody or human immunodeficiency virus (HIV) I and II tests at Screening.
11. Positive for drugs of abuse, nicotine/cotinine or alcohol on Screening or (each) admission.
12. Use of any investigational drug in any clinical trial within 90 days from the last administration, or on extended follow-up in a clinical trial, even if the last administration of an IMP was > 90 days ago.

13. Donation or loss of more than 450 mL of blood in the 90 days prior to Screening.
14. Excessive consumption of xanthine-containing food or beverages (> 5 cups of coffee per day or equivalent) or inability to stop consuming caffeine, from 48 hours prior to IMP administration until 48 hours after IMP administration.

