8.5.2 Analysis of Primary Endpoints

8.5.2.1 Safety

Part A and Part B

Safety data analysis will be conducted on the Safety Analysis Set. The number and percentage of subjects experiencing one or more AEs will be summarized by dose level group, relationship to IMP, and severity. AEs will be coded using Medical Dictionary for Regulatory Activities terminology. Laboratory parameters will be summarized using descriptive statistics, by postdose shifts relative to baseline, and data listings of abnormal results as appropriate. Vital signs and ECG data will be summarized for observed and changes-from-baseline values by dose level using descriptive statistics. Clinically noteworthy ECG findings for individual subjects will be listed and summarized as appropriate.

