# Presentation of Continuous and Qualitative Variables for Demographics, Other Baseline Characteristics, and Safety

Continuous variables will be summarized using descriptive statistics, ie:

- number of subjects, number of subjects with non-missing values
- mean, standard deviation (SD)
- median, 25th Percentile 75th Percentile (Q1-Q3)
- minimum (Min) and maximum (Max).

Qualitative variables will be summarized by counts and percentages.

Unless otherwise stated, the calculation of proportions will be based on the number of subjects in the analysis set of interest. Therefore, counts of missing observations will be included in the denominator and presented as a separate category.

When the analysis refers only to certain visits, percentages will be based on the number of subjects still present in the study at that visit, unless otherwise specified.

Mean, Median, Q1, Q3, Min, and Max will have the same precision as collected for SDTM datasets for non-derived data. Standard deviation will be presented with one digit more than the mean. Statistics on derived data will be rounded to reasonable digits whereas maximal digits should be

available in Analysis Data Model (ADaM) datasets. Percentage and percent change from baseline will be reported using 1 decimal digit, if not otherwise specified.

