# 15.4 Vital Signs

Vital signs data will be summarized by dose and time point using descriptive statistics for baseline (see definition in Section 9), each evaluation during the study, and change from baseline to each evaluation. Listing of vital signs data will be provided.

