# 15.5 Other Safety or Tolerability Evaluations

# 15.5.1 12-lead Electrocardiogram

Safety ECG data will be summarized by dose and time point using descriptive statistics for baseline (see definition in Section 9), each evaluation during the study, and change from baseline to each evaluation. Listing of safety ECG data will be provided.

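### The vital-sign and ECG endpoint is an incidence, but SAP 15.4 and 15.5.1 plan no count of affected subjects, and the protocol's summary of noteworthy ECG findings is dropped without being declared

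*SAP*

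**What the plan says.** SAP Section 5 lists three primary endpoints for Part A. The third is "Incidence of clinically significant changes and abnormalities in vital signs (body temperature, BP, heart rate, and respiratory rate) and 12-lead ECG", and it is referred to SAP 15. The same endpoint is secondary in Part C.

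SAP 15.4 plans: "Vital signs data will be summarized by dose and time point using descriptive statistics for baseline", each later evaluation and change from baseline, and then "Listing of vital signs data will be provided". SAP 15.5.1 uses the same pattern: "Safety ECG data will be summarized by dose and time point using descriptive statistics for baseline", followed by "Listing of safety ECG data will be provided". SAP 9 defines the descriptive statistics as counts of subjects and of non-missing values, mean, SD, median, quartiles, minimum and maximum.

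Protocol 8.5.2.1 plans descriptive statistics for vital signs and ECG. For ECG it adds: "Clinically noteworthy ECG findings for individual subjects will be listed and summarized as appropriate". The SAP text has no counterpart to that sentence. SAP 7, which records changes from the protocol, names only the removal of the 0-24 h AUC parameters and the addition of a dried-blood-spot correlation.

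**The concern.** An incidence is a count of subjects with an event over the subjects at risk. The two SAP subsections that handle these data define no event and count no subjects. Followed as written, they describe the distribution of values at each time point and leave the stated endpoint without its own result.

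Two things are at stake. First, SAP 4 says that analyses not identified in the plan will be marked as unplanned in the study report. An incidence table added later for a primary safety endpoint of a first-in-human trial would therefore be post hoc, with criteria that could be chosen after the Part A code is broken. Second, the one per-subject summary that the protocol did promise, for ECG, has gone without explanation.

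**Working it through.** The plan has no figure to reproduce. It gives no threshold or event rate for a clinically significant vital-sign or ECG change, and Protocol 8.1 states that the Part A sample size has no formal basis. The check compares the texts and then uses assumed values to ask whether the planned tables could yield the endpoint.

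**Step 1. Endpoint against analysis.**

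| Item | Vital signs | ECG |
|---|---|---|
| Endpoint (SAP 5) | Incidence | Incidence |
| Protocol 8.5.2.1 | Descriptive statistics | Descriptive statistics, plus noteworthy findings listed and summarized |
| SAP 15.4 / 15.5.1 | Descriptive statistics, listing | Descriptive statistics, listing |
| Criterion, flag or n (%) in those SAP sections | None | None |
| Change declared in SAP 7 | Not applicable | No |

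For comparison, SAP 15.3 gives laboratory data out-of-range flags and listings of abnormal results. Vital signs and ECG get neither.

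**Step 2. Can the incidence be recovered from per-time-point tables?** Take six active subjects (Protocol 5.2.2, ratio 6:2). Assume a QTcF change of +40 ms at three time points and 0 otherwise.
- Scenario A: the same subject is affected all three times.
- Scenario B: a different subject is affected each time.

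In both scenarios each of the three rows holds the values 40, 0, 0, 0, 0, 0. The mean is 40/6 = 6.7 ms, the SD is 40/√6 = 16.3 ms, the median and quartiles are 0, the minimum is 0 and the maximum is 40. The printed tables are identical. The incidence is 1/6 = 16.7% in A and 3/6 = 50% in B.

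**Step 3. Does the maximum give the count within one time point?** Compare two assumed sets of changes, with an illustrative cut at 60 ms.

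| Changes (ms) | Mean | Q3 | Max | Subjects > 60 ms |
|---|---|---|---|---|
| -6, -3, 0, 2, 4, 65 | 10.33 | 3.5 | 65 | 1 of 6 |
| -6, -3, 0, 2, 62, 65 | 20.00 | 47.0 | 65 | 2 of 6 |

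The maximum reveals that an outlier exists but is the same for one or two affected subjects. The mean and upper quartile move, yet no reader can turn them into a count.

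**Step 4. Unscheduled values.** SAP 9 keeps repeated and unscheduled measurements out of summaries unless a repeat was made for unreliable values or technical reasons. Protocol 7.4.4.1 and 7.4.4.5 allow extra vital signs and ECGs at the investigator's discretion. An abnormality found only there would not reach the maximum. Unless reported as an adverse event, it would appear only in a listing.

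**Step 5. What a count would show.** Exact (Clopper-Pearson) 95% limits:
- 1 of 6: 16.7%, from 0.4% to 64.1%.
- 0 of 6: upper limit 1 − 0.025^(1/6) = 45.9%.
- 0 of 22 pooled placebo, if all 11 Part A cohorts run (11 × 2 = 22): upper limit 1 − 0.025^(1/22) = 15.4%.

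The chance of at least one affected subject among six is 1 − (1 − p)^6. It is 26.5%, 46.9% and 73.8% for assumed true rates of 5%, 10% and 20%.

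**The case against.** The strongest reply is that outliers are not hidden. Minimum and maximum are reported for values and changes, so one subject at +60 ms gives a printed maximum of +60 as well as a mean of 60/6 = 10 ms. A reader might infer that the SAP reports only means, or that outliers vanish from every table. The documents do not support that for scheduled measurements.

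A reader might also infer that such abnormalities are never counted. That is too strong. Protocol 7.4.1.1 sends abnormal findings into adverse event reporting when they are symptomatic, lead to discontinuation or are judged medically important. Protocol 7.4.4.5 treats ECG values outside named reference ranges for AE reporting as clinically relevant. SAP 15.1.1 then counts subjects with treatment-emergent events by system organ class and preferred term. This overlaps with the endpoint but does not replace it. Adverse events are a separate primary endpoint in SAP 5, the SAP does not tabulate the investigator's ECG relevance assessment, and Protocol 7.4.4.1 has no comparable range rule for vital signs.

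Three further limits stand:
- The departure from the protocol concerns ECG only, because the protocol itself planned no vital-sign incidence table. The ECG sentence is also qualified by appropriateness.
- A claim that QTc outliers are counted nowhere cannot be made. The SAP contents list a Section 16.4 on digital ECG whose text is not available here, and the protocol places the digital QTc analysis in a separate report.
- The trial is exploratory, and the Safety Monitoring Committee reviews ECG and vital signs after each cohort, so dose escalation does not hang on this table.

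**Conclusion.** The concern holds in a limited form. The planned vital-sign and ECG analyses cannot produce the incidence that SAP 5 names as a primary endpoint in Part A and a secondary endpoint in Part C. The protocol's summary of noteworthy ECG findings has been dropped without being declared. Step 2 gives the size: the same tables fit an incidence of 16.7% or 50% in a six-subject group. The millisecond values there are assumptions. The conclusion does not depend on them, because statistics computed separately at each time point cannot link values to subjects across time.

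This is a gap in reporting a stated endpoint. It does not show that a safety signal would be missed. With six active subjects per dose, a count carries wide limits and adds description more than inference. It should be corrected, at little cost.

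**What to change.** Add to SAP 15.4 and 15.5.1 a table by dose, with pooled placebo in Part A. It should give n (%) of subjects with at least one post-dose clinically significant abnormality at any time, and should include unscheduled values as a stated exception to SAP 9.

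Base the event on the investigator's assessment and, for ECG, on the reference ranges for AE reporting named in Protocol 7.4.4.5. For vital signs the SAP must say what counts, since the protocol names no such ranges. The sponsor should fix any numeric limits before the Part A code is broken and, as Part C is open-label, before database lock there. The entry limits ("QTcF) > 450 ms, PR > 210 ms, QRSD > 120 ms at Screening and predose", and blood pressure above 140/90 mmHg) are one available reference. They were written for eligibility, and the blood pressure limit would not register low values, so the sponsor may justify others.

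Restore the summary of clinically noteworthy ECG findings, or declare and explain its removal in SAP 7.

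The cost is SAP wording and two tables from collected data. This assumes that the investigator's assessment is recorded in usable form, which the documents do not confirm for vital signs. The downside is that isolated outliers will also appear in placebo subjects, which the pooled placebo column helps the reader to judge.
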